8.4 Grading of the Severity of an Adverse Event

The severity of adverse events will be graded using the Common Terminology Criteria for Adverse Events (CTCAE), Version 4.03 (available at http://evs.nci.nih.gov/ftp1/CTCAE/CTCAE_4.03_2010-06-14_QuickReference_8.5x11.pdf). For each episode, the highest severity grade attained should be reported.

If a CTCAE criterion does not exist, the investigator should use the grade or adjectives: Grade 1 (mild), Grade 2 (moderate), Grade 3 (severe), Grade 4 (life-threatening), or Grade 5 (fatal) to describe the maximum intensity of the adverse event. For purposes of consistency with the CTCAE, these intensity grades are defined in Table 1.

Table 2. Grading of Adverse Event Severity

Grade	Adjective	Description
Grade 1	Mild	Sign or symptom is present, but it is easily tolerated, is not expected to have a clinically significant effect on the subject's overall health and well-being, does not interfere with the subject's usual function, and is not likely to require medical attention.
Grade 2	Moderate	Sign or symptom causes interference with usual activity or affect clinical status, and may require medical intervention.
Grade 3	Severe	Sign or symptom is incapacitating or significantly affects clinical status and likely requires medical intervention and/or close follow-up.
Grade 4	Life-threatening	Sign or symptom results in a potential threat to life.
Grade 5	Fatal	Sign or symptom results in death.

The distinction between the seriousness and the severity of an adverse event should be noted. Severe is a measure of intensity; thus, a severe reaction is not necessarily a serious reaction. For example, a headache may be severe in intensity, but would not be classified as serious unless it met one of the criteria for serious events listed in Section 8.1.2 above.

8.5 Describing Adverse Event Relationship to Study Drug and Study Procedures

The relationship of an adverse event to study drug should be assessed using clinical judgment, describing the event as either unrelated (no) or related (yes) consistent with the following definitions:

- **No:** Evidence exists that the adverse event had an etiology other than the study drug. For serious adverse events, an alternative causality must be provided (e.g., pre-existing condition, underlying disease, intercurrent illness, or concomitant medication).
- **Yes:** A temporal relationship exists between the adverse event onset and administration of the investigational medicinal product that cannot be readily explained by the subject's clinical state or concomitant therapies. Furthermore, the adverse event appears with some degree of certainty to be related to the study drug based on the known therapeutic and pharmacologic actions or adverse event profile of the investigational medicinal product. In case of cessation or reduction of the dose, the adverse event abates or resolves. In case of interruption and rechallenge, the event reappears upon rechallenge.

Of note, even in circumstances when the study drug is given intermittently or is interrupted temporarily before the onset of the adverse event, consideration should be given as to whether the study drug may have contributed to the event.

The relationship to protocol-mandated study procedures (e.g., procedures such as venipuncture or performance of an electrocardiogram) should be assessed using the following considerations:

- No: Evidence exists that the adverse event has an etiology other than the study procedure.
- Yes: The adverse event occurred as a result of a protocol-mandated procedure.

8.6 Adverse Event Reporting Requirements

8.6.1 Site Reporting Requirements

Classification of an event as serious or nonserious (see Section 8.1.2) determines the reporting procedures to be followed by the site.

Site reporting requirements for adverse events are summarized in Table 3 below.

Table 3. Site Reporting Requirements for Adverse Events

Classification	Reporting Time	Reporting Action
Serious	Within 24 hours	Submit the designated serious adverse event report form to sponsor or designee, and to the site IRB, as per local IRB requirements; include copies of relevant source documents (e.g., progress notes, autopsy reports, laboratory and diagnostic test results, discharge summaries)
	Within 24 hours	Telephone call or e-mail to the study sponsor medical monitor ^a
	Per eCRF submission procedure	Record and submit information on appropriate CRFs
Nonserious	Per eCRF submission procedure	Record and submit information on appropriate CRFs

^a See Safety Management Plan and Site Study Binder for study contact information
Abbreviations: eCRF=electronic case report form, IRB=institutional review board

For serious adverse events, the Serious Adverse Event Report Form must be completed in addition to completing the adverse event portion of the CRF. The information in the adverse event portion of the Serious Adverse Event Report Form(s) and CRF must match or be reconciled. Where the same data are collected, the forms must be completed in a consistent manner. For example, the same adverse event term should be used on both forms.

Particularly for fatal or life-threatening events, copies of progress notes, autopsy reports, laboratory and diagnostic test results, discharge summaries, and other relevant documents should be e-mailed or faxed when requested and applicable. Follow-up information to the serious adverse event should be clearly documented as “follow up” in the serious adverse event report form and must be faxed or emailed to these same parties. The study sponsor may request additional information from the investigator to ensure the timely completion of accurate safety reports.

The subject's name, address, and other personal identity information should be obscured on any source documents (e.g., progress notes, nurses' notes, laboratory and diagnostic test results, discharge summaries) but without losing the traceability of a document to the study subject identifiers. Only the subject's study number, initials, or date of birth are to be provided.

In the rare event that the investigator does not become aware of the occurrence of a serious adverse event immediately (for example, if a subject initially seeks treatment elsewhere), the investigator is to report the event within 24 hours after learning of it and to document his/her first awareness of the adverse event.

Contact details for the study sponsor medical monitor will be provided in the Safety Management Plan and Site Study Binder.

8.6.2 Study Sponsor Reporting Requirements

Each serious adverse event report received from the investigator must be evaluated by the investigator as well as the study sponsor medical monitor. Each is required to review all unanticipated problems involving risk to subjects or others, serious adverse events, and all subject deaths associated with the protocol and provide an unbiased written report of the event. At a minimum, the study sponsor medical monitor should comment on the outcomes of the event or problem, and in the case of a serious adverse event or death, comment on the relationship to participation in the study. The designated study sponsor medical monitor should also indicate whether they concur with the details of the report provided by the study investigator.

For regulatory reporting purposes, the event is classified as related if any of the investigator or study sponsor medical monitor determines that the event is related to the study drug (see Section 8.5). For reporting purposes, an adverse event will be considered expected if the study sponsor determines that the event is expected (see Section 8.2).

The study sponsor awareness date will be used in determining adverse event regulatory reporting timelines. The study sponsor awareness date is defined as the earliest date the study sponsor or an agent (e.g., a site monitor) becomes aware of an adverse event. This is the date the regulatory reporting clock begins and the date is considered Day 0.

The study sponsor serious adverse event regulatory reporting requirements are described in Table 4.

Table 4. Study Sponsor Reporting Requirements for Adverse Events

Type of Event			Type of Report	Timeframe for Reporting To Health Authorities
Fatal or Life-Threatening	Unexpected	Related		
Yes	Yes	Yes	Letter notification (may also include CIOMS I/MedWatch form)	Within 7 calendar days of study sponsor awareness date or according to local regulations
			CIOMS I/MedWatch form	Within 15 calendar days of study sponsor awareness date or according to local regulations
No	Yes	Yes	CIOMS I/MedWatch form	Within 15 calendar days of study sponsor awareness date or according to local regulations
Yes	No	Yes	Annual report	Annually
No	No	Yes		
Yes	Yes	No		
No	Yes	No		
Yes	No	No		
No	No	No		

Abbreviations: CIOMS= Council for International Organizations of Medical Sciences

If notification of an adverse event requiring expedited reporting is received, the study sponsor (or designees) will contact each clinical investigator prescribing RX-0201 by e-mail, fax, or overnight mail such that the investigator can promptly notify the site IRB (within 7 calendar days for deaths or life-threatening events or within for 15 calendar days for other reportable events from the study sponsor awareness date). All unanticipated problems involving risk to subjects or others, serious adverse events related to participation in the study, and subject deaths related to participation in the study will also be promptly reported via telephone, facsimile, or e-mail by the study sponsor (or designees) to appropriate health regulatory authorities.

8.7 Special Situation Reporting Requirements

8.7.1 Definitions of Special Situations

Special situation include pregnancy; medication error, abuse, misuse, or overdose.

- Information regarding pregnancy is provided in Section 8.7.2.
- A medication error is any preventable event that can cause or lead to inappropriate medication use or subject harm while the medication is in the control of a healthcare professional or subject.
- Abuse is defined as persistent, sporadic or intentionally excessive use of a drug by a subject when such use is accompanied by harmful physical and/or psychological effects.

- Misuse is defined as any use of a drug in a way that is not in accordance with the protocol instructions and may be accompanied by harmful physical and/or psychological effects.
- An overdose is defined as a dose taken (accidentally or intentionally) that meets the criteria for overdose prescribed by the protocol (see Section 6.1.3). In cases of a discrepancy in drug accountability, overdose will be established only when it is clear that the subject has taken excessive amounts of drug or the investigator has reason to suspect that the subject has taken excessive amounts of drug.

8.7.2 Pregnancy

The following safety reporting instructions related to pregnancy are included as a precaution.

Each female subject should be instructed to discontinue further study therapy and inform the investigator immediately if she becomes pregnant at any time between the first dose of study drug until 30 days after the last ingestion of study drug.

Each male subject should be instructed to inform the investigator immediately if he impregnates a woman at any time between the 1st dose of study drug until 30 days after the last ingestion of study drug

The investigator should counsel the subject regarding the possible effects of investigational medicinal product exposure on the fetus and the need to inform the study site of the outcome of the pregnancy.

Neither a pregnancy itself nor an induced elective abortion to terminate the pregnancy without medical reasons is considered an adverse event; such occurrences should be reported on the appropriate pregnancy reporting forms. However, if the outcome of the pregnancy meets the criteria for classification as a serious adverse event (i.e., spontaneous abortion, induced abortion due to complications, stillbirth, neonatal death, or congenital anomaly [including that in an aborted fetus]), the investigator should follow the procedures for reporting serious adverse events, i.e., report the event to the sponsor or designee by telephone and follow up by submission of the appropriate adverse event CRFs (see Section 8.6.1).

Additional information regarding reporting pregnancy outcomes may be required:

- Any spontaneous abortion, including miscarriage and missed abortion will be reported as a serious adverse event.
- An induced therapeutic abortion to terminate any pregnancy due to complications or other medical reasons will be recorded as a serious adverse event. The underlying medical reason for this procedure should be recorded as the adverse event term.

- All neonatal deaths that occur within 1 month of birth should be reported, without regard to causality, as serious adverse events. In addition, any infant death after 1 month that the investigator assesses as related to the in-utero exposure to the study drug should also be reported.
- In the case of a live birth, the “normality” of the newborn can be assessed at time of birth (i.e., there is no required minimum follow-up of a presumably normal infant before the Pregnancy Outcome Report CRF can be completed).
- The “normality” of an aborted fetus can be assessed by gross visual inspection unless there are pre-abortion laboratory findings suggestive of a congenital anomaly, in which case pathologic examination should be requested.

Information regarding any pregnancy in a study subject or the female partner of a male subject must be documented on a Pregnancy Reporting Form and forwarded to the sponsor or designee within 24 hours of learning of the pregnancy. Monitoring of the pregnancy in both female study subjects and female partners of male study subjects should continue until the conclusion of the pregnancy. The outcome of the pregnancy should be reported on the Pregnancy Outcome Report Form within 5 days of the conclusion of the pregnancy. If the end of the pregnancy occurs after the study has been completed, the outcome should be reported directly to the study sponsor.

8.7.3 Instructions for Reporting Special Situations

Along with information regarding the circumstances of the special situation, any clinical sequelae occurring in association sequelae with that situation should be reported as adverse events or serious adverse events according to the reporting requirements for those events (see Section 8.6). Details of signs or symptoms, clinical management and outcome should be reported, if available.

8.8 Other Events Requiring Rapid Reporting

DLTs are events [toxicities] specifically identified in this protocol that must be reported to the Sponsor or designee in an expedited manner in Stage 1. Information regarding DLTs should be recorded on a protocol-designated DLT report form and sent to the study sponsor or designee within 24 hours of site personnel becoming aware of the event. DLTs may or may not be serious adverse events as defined in this protocol but may be serious adverse events if they meet one or more of the criteria for a serious adverse event (see Section 8.1.2). If a DLT is also a serious adverse event, it should be reported both on the DLT report form and per the

instructions for reporting serious adverse events (see Section 8.6.1). Recording of a DLT in the relevant CRFs will also be required.

9. STATISTICAL CONSIDERATIONS

9.1 Study Design

9.1.1 Stage 1

Stage 1 is a dose escalation study to determine the MTD up to a target dose of 250 mg/m²/day of RX-0201 in combination with everolimus. The starting dose of RX-0201 will be 125 mg/m²/day. The secondary objectives of Stage 1 of the study are described in Section 1.2.

9.1.2 Stage 2

Prior to starting Stage 2, the principal investigators, medical monitor and sponsor will review the safety, laboratory and dosing information to make decisions regarding the start of Stage 2. Approximately 20 additional subjects will be treated with the combination of everolimus and RX-0201. The primary objective of Stage 2 is to determine progression free survival. The primary analysis will be conducted approximately 6 months after the last enrolled subject is treated. The secondary objectives of Stage 2 of the study are described in Section 1.2.

9.2 Study Endpoints, Subsets, and Covariates

9.2.1 Study Endpoints

9.2.1.1 Primary Endpoints

- Incidence of adverse events and clinical laboratory abnormalities defined as dose-limiting toxicities (Stage 1)
- Progression free survival at 4.5 months (Stage 2)

9.2.1.2 Secondary Endpoints

- Pharmacokinetics profile of RX-0201 (Stage 1)
- Incidence of adverse events, changes in clinical laboratory tests and vital signs over time (Stage 1 and Stage 2)
- Tumor response, duration of response, time to response, and response rates (Stage 2)

9.2.1.3 Exploratory endpoints

- Blood levels of AKT pathway biomarkers, tumor apoptosis biomarkers or other biomarkers (Stage 1 and Stage 2)
- Plasma concentration of RX-0201 at the end of infusion (Stage 2)

9.2.2 Analysis Populations

Data from stages 1 and 2 of this study will be combined for both safety and efficacy analyses when appropriate. The following definitions of the various analysis sets to be used will therefore be applied to subjects in Stage 1 and Stage 2 of the study.

Safety Analysis Set:

The safety analysis set includes all subjects who receive at least one dose of study drug(s) with subjects analyzed according to the treatment received. All safety data will be analyzed in accordance with this analysis set.

Full Analysis Set:

The Full Analysis set includes all enrolled or randomized subjects with subjects analyzed according to the treatment assigned at enrollment/randomization. All efficacy endpoints will be analyzed using the Full Analysis set.

Per Protocol Analysis Set:

The Per-Protocol Analysis set will include all subjects without pre-specified major protocol deviations. Sensitivity analyses of some efficacy endpoints may be performed using the per-protocol analysis set.

Evaluable for Tumor Response Analysis Set (Stage 2 only):

The tumor response analysis set will include all subjects in the Full Analysis Set (and Per-Protocol Set if applicable) with a uni-dimensional measurable lesion at baseline (as per RECIST ver. 1.1).

9.2.3 Covariates

If appropriate based on sample size, the following covariates may be used to examine selected safety and efficacy endpoints in subgroups or in multivariate analyses.

- Sex: Male and Female
- Age: < 65, ≥ 65 to ≤ 75, > 75
- ECOG: 0 or 1 or 2

9.3 Sample Size Considerations

Approximately 9 subjects will be enrolled in Stage 1 of the study. Stage 1 is designed to determine the MTD up to a target dose of 250 mg/m²/day of RX-0201, thus the sample size for the study is not based on a formal statistical hypothesis but will be determined based on observed number of first-cycle DLTs at each dose level. The sequential 3+3 dose-escalation is

consistent with usual oncologic paradigms for dose ranging as the intent is to limit the number of subjects who are exposed to toxic doses of the treatment combination. The trial will use the standard National Cancer Institute (NCI) definition of MTD (starting dose associated with DLT in < 33.3% of subjects during the first cycle of therapy).

The planned sample size for Stage 2 is approximately 10 subjects in the everolimus arm and 20 subjects in the everolimus/ RX-0201 arm. The primary goal is to provide preliminary estimates of safety and efficacy endpoints when combining everolimus and RX-0201. Safety endpoints will be reported as described in Section 8. The primary efficacy endpoint is progression free survival estimated using the Kaplan-Meier method and associated 90% confidence intervals. Median PFS is expected to be 4.5 months in the everolimus only arm and 9 months in the combination arm. With 10 evaluable subjects in the everolimus only arm the width of the two-sided 90% confidence interval for 9-month PFS will be no more than ± 0.28 . With 20 evaluable subjects in the combination arm the width of the two-sided 90% confidence interval for 9-month PFS will be no more than ± 0.20 .

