This study will be a 2-stage multi-center, open-label study to assess the safety and tolerability of

RX-0201 in combination with everolimus versus everolimus alone to treat subjects with advanced renal cell carcinoma

- Stage 1 will be an open-label, dose-escalation study of RX-0201 to identify a safe and tolerable dose of RX-0201 up to a target dose of 250 mg/m²/day when given in combination with everolimus.
- Stage 2 will be an open-label, 2-arm study of RX-0201 in combination with everolimus versus everolimus alone. Subjects will receive RX-0201, at the dose identified in Stage 1, in combination with everolimus for up to 8 cycles to determine safety and efficacy of the combination.

Sample Size:

Stage 1; n = approximately 9 subjects will be enrolled in Stage 1 to receive the combination of everolimus (10 mg) and RX-0201 at increasing doses of RX-0201 to the MTD or up to a target dose of 250 mg/m²/day.

Stage 2; n = approximately 23 subjects will be treated with everolimus and RX-0201.

Study Centers: Up to 20 sites in the United States

Summary of Subject Eligibility Criteria:

Inclusion Criteria

Disease Related

- Documented histological or cytological diagnosis of renal cell cancer with a clear-cell component
- Measurable or evaluable disease defined by Response Evaluation Criteria for Solid Tumors (RECIST) ver. 1.1
- Must have received at least one course of therapy with a VEGFR-targeting tyrosine kinase inhibitor (eg, sorafenib, sunitinib, axitinib, pazopanib or tivozanib) and progressed within 6 months of planned first dose of study treatment
- Prior therapy with cytokines (i.e., IL-2, Interferon) and/or VEGF-ligand inhibitors (i.e., bevacizumab) are permitted
- Prior vaccine therapy in the adjuvant setting is permitted
- Tissue blocks or tissue sections from initial diagnosis or upon diagnosis of advanced metastatic disease will be available for submission to the central laboratory within approximately 4 weeks after initiation of study treatment; exceptions (eg, histology determined by fine needle aspirate or tissue is no longer available) require written documentation of why a sample is not available and prior approval by the sponsor before enrollment/ randomization
- ECOG performance status of 0,1 or 2
- Life expectancy > 3 months

Demographic

- Males and females ≥ 18 years of age at screening

Ethical

- Before any study-specific procedures are performed, the appropriate written informed consent must be obtained

Exclusion Criteria

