The primary objective of Stage 1 will be to determine the dose of RX-0201 to be administered in combination with 10 mg of everolimus. Approximately 9 subjects will be enrolled in Stage 1 to be treated with everolimus and increasing doses of RX-0201 up to a target dose or the MTD.

After the dose of RX-0201 is determined in Stage 1, Stage 2 will begin accrual.

Stage 2 will now be an open label study enrolling approximately 20 subjects with the dose of RX-0201 selected in Stage 1 in combination with everolimus. The primary objective of Stage 2 will be to assess progression free survival as determined by imaging assessments after every 2 cycles of treatment (i.e., approximately every 6 weeks).

Other than the safety evaluation required to determine whether to proceed to Stage 2, no planned formal interim analysis will be performed.

All reported adverse events will be assigned a body system, and preferred term within a body system, according to the current version of MedDRA the adverse event preferred term dictionary. The number and percent of subjects reporting adverse events (all, serious, and related) will be tabulated by treatment.

Study Glossary

Term	Definition
AE	Adverse Event
ALT	Alanine Aminotransferase
AKT	Protein Kinase B
ANC	Absolute Neutrophil Count
AST	Aspartate Aminotransferase
CT	Computed Tomography
CTCAE	Common Terminology Criteria for Adverse Events
DLT	Dose Limiting Toxicity
DMP	Data Management Plan
ECOG	Eastern Cooperative Oncology Group
eCRF	Electronic Case Report Form
GCP	Good Clinical Practice
ICH	International Conference on Harmonisation
INR	International Normalization Ratio
IRB	Institutional Review Board
MedDRA	Medical Dictionary for Drug Regulatory Activities
MRI	Magnetic Resonance Imaging
MTD	Maximum Tolerated Dose
PT	Prothrombin Time
PTT	Partial Thromboplastin Time
RCC	Renal Cell Carcinoma
RECIST	Response Evaluation Criteria in Solid Tumors
TKI	Tyrosine Kinase Inhibitor
ULN	Upper Limit of Normal
VEGF	Vascular Endothelial Growth Factor
WHO	World Health Organization

Table of Contents

	Page
Protocol Synopsis.....	3
Study Glossary	8
1. OBJECTIVES	13
1.1 Primary.....	13
1.2 Secondary.....	13
1.3 Exploratory:.....	13
2. BACKGROUND AND RATIONALE.....	13
2.1 Disease and Treatments	13
2.2 AKT and Cancer.....	14
2.3 RX-0201 Background.....	15
2.3.1 Nonclinical Studies	15
2.3.2 Prior Clinical Experience.....	16
3. EXPERIMENTAL PLAN.....	17
3.1 Study Design.....	17
3.2 Number of Centers	18
3.3 Number of Subjects.....	18

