As of 06 March 2017, nine subjects have been randomized and treated in the Phase 2 portion of the study. The treatment of metastatic renal cell carcinoma and recruitment for this study have been significantly impacted by the approval of 3 new therapies (nivolumab, cabozantinib, and lenvatinib + everolimus). Treatment with everolimus alone in the clinical study setting is no longer a preferred option for clinicians and patients. Therefore, the everolimus alone treatment arm and randomization component is being removed in this protocol amendment.

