3.3 Number of Subjects

In Stage 1 approximately 9 subjects will be enrolled to receive escalating doses of RX-0201 in combination with everolimus. The number of subjects enrolled into Stage 1 will vary depending upon the number of dose levels needed to determine the MTD up to a target dose of 250 mg/m²/day of RX-0201.

In Stage 2 approximately 23 subjects will be treated (i.e., 3 subjects in the everolimus arm and up to 20 subjects in the everolimus/RX-0201 arm).

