## **6 Sample Size**

Sample size calculation for this study has been empirically set. Approximately 32 subjects will be recruited and enrolled into the study over 20 centers in the US.

For Stage 1, approximately 9 subjects will be enrolled in to receive the combination of everolimus (10 mg) and RX-0201 at increasing doses of RX-0201 to the MTD or up to a target dose of 250 mg/m^2/day. For Stage 2, approximately 3 additional subjects will be treated with everolimus alone arm and up to 20 subjects in the everolimus/RX-0201.

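### Protocol 9.3 still sizes Stage 2 for 10 everolimus-alone subjects with 90% intervals; the current plan has 3, uses 95% intervals, and states no precision for the 4.5-month primary endpoint

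*Protocol*

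**What the plan says.** **Protocol 9.3.** "The planned sample size for Stage 2 is approximately 10 subjects in the everolimus arm", with 20 in the combination arm. It calls for Kaplan-Meier estimation of PFS with 90% intervals and expects median PFS of 4.5 months on everolimus alone and 9 months on the combination. Its precision statement, beginning "With 10 evaluable subjects in the everolimus only arm the width of the two-sided 90% confidence interval for 9-month PFS", gives at most ±0.28 for 10 controls; the next sentence gives at most ±0.20 for 20 combination subjects, also for 9-month PFS.

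**Arm sizes elsewhere.** Protocol 2.3.2 says that "the everolimus alone treatment arm and randomization component is being removed in this protocol amendment". Protocol 5.3 assigns all Stage 2 subjects to the combination. Protocol 3.3 counts "3 subjects in the everolimus arm and up to 20 subjects in the everolimus/RX-0201 arm". SAP 6 agrees: "approximately 3 additional subjects will be treated with everolimus alone arm and up to 20 subjects in the everolimus/RX-0201". It also gives the study total: "Approximately 32 subjects will be recruited and enrolled into the study".

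**Endpoint and confidence level elsewhere.** Protocol 9.2.1.1 and SAP 4.2 and 4.3 make PFS at 4.5 months the primary Stage 2 endpoint. Protocol 9.5.2.3 specifies 95% intervals for landmark PFS. SAP 7.3.5 sets 95% for all intervals, and SAP 9.1.1 uses 95% for PFS quartiles.

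**Synopsis.** The Sample Size entry says "approximately 23 subjects will be treated with everolimus and RX-0201". The Statistical Considerations entry says "Stage 2 will now be an open label study enrolling approximately 20 subjects", all on the combination.

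**The concern.** Section 9.3 holds the only numerical statement of what Stage 2 can estimate; SAP 6 says only that the size was set empirically. Since 9.3 gives preliminary estimation as the primary goal, the precision statement is in effect the justification for the size. If its inputs are not those of the current plan, a report author could quote a control-arm precision that 3 subjects cannot deliver. The author would also find two confidence levels for PFS in the same protocol, and no stated precision at the primary time point. The synopsis adds a smaller mismatch, because 23 is the sum of both arms (3 + 20) but is attached to the combination alone.

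**Working it through.** **Inputs.** From Protocol 9.3: n = 10 and 20, 90% two-sided, bounds 0.28 and 0.20, expected combination median 9 months. From Protocol 3.3 and SAP 6: n = 3 and up to 20. From Protocol 9.5.2.3 and SAP 7.3.5: 95% two-sided.

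**Counts.** With about 9 subjects in Stage 1, Section 9.3 implies 9 + 10 + 20 = 39 subjects. Section 3.3 and SAP 6 imply 9 + 3 + 20 = 32, the total that SAP 6 states.

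**Formula.** For x progression-free out of n with no censoring, the exact (Clopper-Pearson) limits are:

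- lower = Beta quantile at α/2 with parameters (x, n − x + 1), or 0 if x = 0
- upper = Beta quantile at 1 − α/2 with parameters (x + 1, n − x), or 1 if x = n
- half-width = (upper − lower)/2

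**Step 1: reproduce the printed figures (90%).** At 5/10 the interval is 0.222 to 0.778, half-width 0.278, which rounds to 0.28. At 10/20 it is 0.302 to 0.698, half-width 0.198, which rounds to 0.20. These are the largest values over all counts. A Wald interval at p = 0.5 gives 0.260 and 0.184, and Wilson gives 0.231 and 0.173, so the exact method is the one that matches both printed figures.

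**Step 2: put in the current inputs.**

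| Arm | n | Level | Half-width over possible counts | Printed in 9.3 |
|---|---|---|---|---|
| Everolimus alone | 3 | 90% | 0.316 (0/3, 3/3) to 0.424 (1/3, 2/3) | 0.28 (n = 10) |
| Everolimus alone | 3 | 95% | 0.354 to 0.449 | 0.28 (n = 10, 90%) |
| Combination | 20 | 95% | at most 0.228 (10/20: 0.272 to 0.728) | 0.20 (90%) |

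With 3 subjects, every possible count exceeds 0.28 even at the 90% level. With 20 subjects at 95%, every count from 5/20 to 15/20 exceeds 0.20; the half-width is 0.202 at both ends of that range.

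**Step 3: a likely value at 4.5 months.** Assume exponential PFS with the protocol's 9-month median. Then S(4.5) = 0.5^(4.5/9) = 0.707, and 0.707 × 20 ≈ 14. At 14/20 the exact 95% interval is 0.457 to 0.881, half-width 0.212.

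**Step 4: how far the exact-binomial figure stands in for Kaplan-Meier.** The planned method is Kaplan-Meier, and the SAP names no interval formula for PFS. At 14/20 without censoring, a linear Greenwood 95% interval is 0.499 to 0.901 and a log-log interval is 0.451 to 0.853, each with half-width 0.201. The exact figure is therefore a slightly conservative approximation when nobody is censored. Censoring before 4.5 months will generally widen the Kaplan-Meier interval.

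**The case against.** The strongest reply is that little turns on this. The figures are described as supporting preliminary estimates, no test or decision rule uses them, and the SAP is consistent on counts, time point and level. The everolimus-alone arm is closed, and the combination arm keeps its 20 subjects, with its worst-case half-width moving only from 0.198 to 0.228. All of that stands. It limits the weight of the point but does not remove the contradiction within the protocol.

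A reader might infer more than the documents support, in five ways.

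- *That the arithmetic in 9.3 is wrong.* It is not; both bounds reproduce for their stated inputs.
- *That the 9-month landmark invalidates the bounds.* They are maxima over all counts, so moving to 4.5 months changes neither. Nor does 9.3 call 9-month PFS the primary endpoint. The gap is that nothing is stated for 4.5 months.
- *That nothing signals the change.* Protocol 2.3.2, 3.3, 5.3 and 9.1.2, the synopsis and SAP 6 all show that the control arm has changed; only 9.3 was left behind.
- *That SAP 11 is wrong to record no changes.* The 95% level, the 4.5-month endpoint and the count of 3 are all in the protocol already, so that entry is defensible.
- *That controls could never be followed to 9 months.* Eight 21-day cycles come to 168 days (about 5.5 months), so on schedule they would not be. But cycles may lengthen for recovery without a stated cap (Protocol 6.1.2), and a safety visit follows 30 (+7) days after the last dose, so the documents do not rule it out.

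**Conclusion.** The point holds as an inconsistency that should be corrected. Section 9.3 gives a control size (10 against 3) and a confidence level (90% against 95%) that other current text contradicts, and no precision is stated for the primary endpoint. The control-arm bound of 0.28 cannot be met with 3 subjects at either level. The combination-arm bound becomes 0.228 in place of 0.20, or about 0.21 at 14/20. The half-widths assume exact-binomial intervals with no censoring; the 14/20 case also assumes exponential PFS with a 9-month median. The amendment explains the control-arm change; the documents do not show where the 9-month and 90% choices came from. The consequence is limited to describing and reading the estimates: patients, data and the planned analysis are unaffected.

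**What to change.** Restate Protocol 9.3 for 3 everolimus-alone and up to 20 combination subjects, PFS at 4.5 months and 95% intervals. Suggested text:

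> With 20 combination subjects evaluable and uncensored at 4.5 months, the exact-binomial 95% half-width is at most 0.23 (about 0.21 at 14/20). This approximates the planned Kaplan-Meier interval, and censoring will generally widen it.

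Delete the 10-subject control size and the two 9-month precision sentences. Keep the assumption of a 9-month median for the combination. Claim no precision for the 3 everolimus-alone subjects. Correct the synopsis Sample Size entry so that its 23 reads as 3 + 20, in line with Section 3.3.

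The cost is wording and a slightly less favourable combination-arm figure (0.23 for 0.20); no subjects or procedures are added. Under Protocol 12.1 an amendment needs written regulatory and IRB approval unless it is administrative, and the documents do not say which this would be. If the protocol is not to be amended again, put the same statement in SAP 6, accepting that the protocol text then stays uncorrected.
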